### 12.2.2 Primary efficacy variable

The primary null hypothesis to be tested is that the different doses of zolmitriptan 0.5 mg, 2.5 mg and 5 mg are not different from placebo, using pain-free status at 2 hours post treatment as the primary variable.

The primary variable will be analyzed using a logistic regression model with 2-hour pain-free status as the response variable including treatment and center as fixed factors in the model. A step-down approach is used for maintaining the alpha level when comparing the 3 doses of zolmitriptan against placebo for 2-hour pain-free status. Initially, zolmitriptan 5 mg is compared with placebo in terms of odds ratio. If zolmitriptan 5 mg is significantly better than

placebo at the 2-sided 5% level, then zolmitriptan 2.5 mg is compared with placebo, and if it is significantly better than placebo at the 2-sided 5% level, then zolmitriptan 0.5 mg is compared with placebo. If the first comparison between zolmitriptan 5 mg and placebo is not significant, then the zolmitriptan 2.5 mg is not to be compared with placebo, etc. The primary analysis will be based on the FAS with the LOCF approach.

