#### **International Co-ordinating Investigator**

#### **Study centre(s) and number of subjects planned**

This will be a global, multicenter study conducted in the United States (US), Latin America, and Europe. A sufficient number of male and female adolescent patients, age 12 to 17 years with an established diagnosis of migraine, will be screened to ensure that approximately 1000 patients (312 in the zolmitriptan 5 mg and placebo arms) are randomized into the study to obtain 800 evaluable patients (250, 150, 150, and 250 patients in the placebo, zolmitriptan 0.5 mg, zolmitriptan 2.5 mg, and zolmitriptan 5 mg treatment groups, respectively). Based on the results from a blinded interim analysis, the sample size could be increased to obtain a maximum of 1036 evaluable patients. Approximately 150 centers will participate in the study.

---

Study period	Phase of development
Estimated date of first patient enrolled	III
Estimated date of last patient completed	

---

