### 3.1 Overall study design and flow chart

This is a global, multicenter, double-blind, randomized, placebo-controlled study with a parallel group design and single-blind run-in period. The study will comprise treatment of a single attack of migraine headache during the run-in period and placebo challenge with 1 dose of single-blind placebo. If the patient meets conditions for randomization, a single attack of migraine headache will be treated with 1 dose of zolmitriptan nasal spray 0.5, 2.5, 5 mg, or matching placebo in a blinded manner. Approximately 1000 patients will be randomized at approximately 150 study sites in the US, Latin America, and Europe.

Adolescent patients, age 12 to 17 years with an established diagnosis of migraine, as defined by the IHS or IHS-Revised (IHS-R) criteria (see [Appendix D](#)) will be enrolled in the study. Patients will be screened for eligibility during Visit 1 (screening visit) after the informed consent and assent have been obtained. Medical history, migraine headache history and prior medication history will be obtained, and a complete physical examination (including vital sign measurements), 12-lead electrocardiogram (ECG), laboratory assessments (clinical chemistry, hematology and urinalysis), urine drug screen, urine pregnancy test (for all females), and Columbia-Suicide Severity Rating Scale (C-SSRS) will be performed.

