### **12.2 Methods of statistical analyses**

All statistical comparisons will be based on a 2-sided significance level of  $\alpha=0.05$  unless otherwise specified.

Descriptive statistics will be used to present efficacy and safety variables. For continuous variables, n, mean, standard deviation, median, minimum, and maximum will be presented. For categorical variables, n, frequency, and percentage will be presented.

Two types of datasets, both derived from the FAS, will be used for efficacy analyses: the observed case (OC) dataset and the last observation carried forward (LOCF) dataset. In general, the OC data for a visit will consist of the actual observations recorded for the visit. If missing, the OC data will remain missing – no data imputation will be performed. The LOCF data will be the corresponding OC data or, if that is missing, the last non-missing data carried forward from the most recent preceding assessment time. However, baseline values will not be carried forward for LOCF imputation. Baseline is defined as the last non-missing pre-treatment value. No other data imputation will be performed.

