### **12.2.3 Secondary efficacy variables**

The following secondary efficacy variables will be analyzed for OC and/or LOCF in the FAS:

- Pain-free status at 15 minutes and at 1, 2, 3, 4, and 24 hours post treatment;
- Headache response at 15 minutes and at 1, 2, 3, 4, and 24 hours post treatment;
- Sustained headache response at 2 hours subsequent to a 1-hour headache response;
- Presence of associated symptoms of photophobia, phonophobia, or nausea at 15 minutes and at 1, 2, 3, 4, and 24 hours post treatment;
- Resolution of associated symptoms of photophobia, phonophobia, or nausea at 15 minutes and at 1, 2, 3, 4, and 24 hours post treatment;
- Incidence and time to use of rescue medication up to 24 hours post treatment;
- Ability to perform normal activities at 15 minutes and at 1, 2, 3, 4, and 24 hours post treatment.
- Headache recurrence 2 to 24 hours post treatment;
- Bilateral headache (yes/no) at 15 minutes and at 1, 2, 3, 4, and 24 hours post treatment;
- Intensity increased by movement (yes/no) at 15 minutes and at 1, 2, 3, 4, and 24 hours post treatment.

For the binary secondary efficacy variables, the same logistic regression model as for the analysis of primary efficacy variable will be used. Time to use of rescue medication will be displayed graphically using Kaplan-Meier curves by treatment group. Comparison of treatment doses versus placebo will be based on the Cox proportional hazard model. The secondary endpoints will be analyzed at the 2-sided 5% significance level without any multiplicity correction.

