### **12.3 Determination of sample size**

A total of 2400 patients will be enrolled to ensure 1000 randomized patients. This assumes a 56% drop-out rate prior to randomization. Assuming 20% of the randomized patients drop out before treatment of a headache attack, 800 patients (250, 150, 150, and 250 patients in the placebo, zolmitriptan 0.5 mg, zolmitriptan 2.5 mg, and zolmitriptan 5 mg treatment arms, respectively) will be evaluable for the primary analysis. This will give 80% power to detect a treatment difference at the 2-sided significance level of 0.05 if the true difference between a zolmitriptan 5 mg treatment and placebo in terms of difference in pain-free rates is 0.11 for the primary endpoint, 2-hour pain-free status. The power to detect a treatment difference between zolmitriptan 2.5 mg and 0.5 mg versus placebo will be 67% if the true treatment difference is 0.11. A 2-treatment, continuity-corrected, chi-square test of equal proportions is used as an approximation for the intended analysis approach in the power calculations. A difference of 0.11 in response rates is considered a clinically relevant effect. The pain-free rate for the placebo treatment group is assumed to be the same as in a previously conducted study (D1221C00005) on zolmitriptan nasal spray in adolescent patients for both periods combined, 0.18.

Since the assumptions for the sample size calculations are uncertain, an interim analysis is planned for after approximately one third of the planned patients have been treated. The sample size will be re-estimated at the interim analysis using a blinded estimation of the observed total 2-hour pain-free status. The sample size can increase depending on the interim results; the maximum number will be 1036 evaluable patients in total, ie, approximately 1295 patients need to be randomized and 2943 patients need to be enrolled.

The interim analysis will be performed by an independent statistician who is not involved with this trial.

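### Fitting about 150 centers as fixed factors to about 800 patients gives the first primary test a type I error of about 6-7.5% instead of 5%, and exaggerates the odds ratio when there is a true effect

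*Protocol*

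**What the plan says.** Section 12.2.2 specifies a logistic regression for the primary variable, "including treatment and center as fixed factors in the model". The statistical methods part of the synopsis repeats it. The 5 mg dose is tested against placebo first, and the two lower doses are tested only if that comparison succeeds. Section 12.2 sets the level: "All statistical comparisons will be based on a 2-sided significance level of" 0.05.

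On the number of centers, Section 3.1 says "Approximately 1000 patients will be randomized at approximately 150 study sites in the US, Latin America, and Europe", and the synopsis agrees: "Approximately 150 centers will participate in the study". Section 12.3 expects "800 patients (250, 150, 150, and 250 patients in the placebo, zolmitriptan 0.5 mg, zolmitriptan 2.5 mg, and zolmitriptan 5 mg treatment arms" to be evaluable. After sample size re-estimation, "the maximum number will be 1036 evaluable patients in total".

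Section 12.2.3 extends the model: "For the binary secondary efficacy variables, the same logistic regression model as for the analysis of primary efficacy variable will be used". Nowhere does the protocol pool small centers or name a conditional, stratified or random-effects alternative.

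**The concern.** A separate intercept for each center means that the number of nuisance parameters grows with the number of centers while the data per center stay thin. In that setting ordinary maximum likelihood pushes the treatment log odds ratio away from zero, and the model-based standard error does not grow enough to match. Centers in which every patient has the same outcome get an infinite intercept and contribute nothing to the treatment estimate.

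The 5 mg comparison opens the gate to the other doses. If no dose works, nothing can be declared unless this test rejects, so its type I error is the familywise error of the whole sequence. The reported primary odds ratio is affected as well.

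**Working it through.** **Inputs from the protocol.** 150 centers; 800 evaluable patients (250/150/150/250), at most 1036; 1000 randomized with 20% lost before treatment; allocation 5:3:3:5 in center-stratified blocks (Section 5.2.1); two-sided 0.05; difference 0.11; placebo rate taken from an earlier study "on zolmitriptan nasal spray in adolescent patients for both periods combined, 0.18". Hence 0.18 versus 0.29, with odds ratio (0.29/0.71)/(0.18/0.82) = 1.86 and log odds ratio 0.621.

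**The protocol's own figures.** Without continuity correction,

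n = [1.96·√(2·0.235·0.765) + 0.842·√(0.18·0.82 + 0.29·0.71)]² / 0.11² = (1.175 + 0.501)² / 0.0121 ≈ 232.1, so 233 per arm.

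With the correction, n' = (n/4)·[1 + √(1 + 4/(0.11·n))]² = 58.0 × 4.31 ≈ 250. Power is 80.0% for 250 versus 250 and 67.9% for 150 versus 250 (the protocol states 67%). These figures stand. They come from a two-group comparison without a center term, so they cannot reveal the problem.

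**How thin the data are.**
- Evaluable patients per center: 800/150 = 5.3 (1036/150 = 6.9 at the maximum).
- Randomized patients per center: 1000/150 = 6.7. The smallest block that holds the ratio is 5+3+3+5 = 16.
- Expected pain-free patients per center at 0.18: 5.33 × 0.18 = 0.96.
- If centers recruit at equal rates with chance variation, the share with nobody pain-free is exp(-0.96) = 0.38, or about 57 of 150. The simulation found about 59 uninformative centers (39%), leaving about 547 of 800 patients; 253 (32%) carry no information.

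**Simulation of the stated model.** One intercept per center, three dose terms, unconditional maximum likelihood, Wald test of 5 mg versus placebo. Assumed, because the protocol does not give them: blocks of 16, center sizes (equal expected recruitment, or uneven by a gamma distribution), and between-center SD of 0 or 0.5 on the logit scale. There were 5,000 trials per cell, so the Monte Carlo standard error at 5% is √(0.05·0.95/5000) = 0.3 points. Type I error is at 0.18 in all arms; log odds ratio (logOR) and power are at 0.18 versus 0.29 in every dose arm.

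| Recruitment, SD | As written: type I / mean logOR / power | Mantel-Haenszel by center | 15 pooled groups |
|---|---|---|---|
| Equal, 0 | 7.0% / 0.758 / 82.5% | 4.8% / 0.632 / 73.2% | 4.7% / 0.638 / 83.4% |
| Equal, 0.5 | 7.0% / 0.759 / 82.5% | 5.0% / 0.633 / 73.8% | 4.6% / 0.613 / 81.2% |
| Uneven (shape 1), 0 | 6.4% / 0.707 / 80.8% | 4.8% / 0.621 / 74.7% | 4.8% / 0.633 / 82.4% |
| Uneven (shape 1), 0.5 | 6.7% / 0.709 / 81.2% | 4.9% / 0.624 / 75.2% | 5.0% / 0.611 / 80.4% |
| Uneven (shape 0.5), 0 | 6.7% / 0.689 / 81.7% | 5.6% / 0.623 / 76.8% | 5.4% / 0.633 / 82.2% |
| Uneven (shape 0.5), 0.5 | 6.1% / 0.697 / 82.2% | 5.0% / 0.630 / 77.2% | 5.0% / 0.617 / 82.0% |

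Further runs of the model as written:
- Equal recruitment, 10,000 trials: 7.7% (likelihood ratio 7.9%).
- Null rate 0.25: 7.4%.
- 100 centers: 6.1-6.8%.
- 1036 patients: 6.3-6.9%.
- Separately programmed replications: 7.3-8.7% with equal recruitment (the 8.7% from 4,000 trials), and mostly 5.7-7.3% with uneven recruitment, 100 centers or 1036 patients. Some smaller runs with skewed sizes fell to 5.2%.

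Pooling to 25 strata gave 5.0-5.8%, a log odds ratio of about 0.64 and power of 82-83%.

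**Odds ratio.** As written: exp(0.689) = 1.99 to exp(0.759) = 2.14, against 1.86. On the log scale this is 0.689/0.621 = 1.11 to 0.759/0.621 = 1.22, so 11-22% too large. Under the null the mean log odds ratio was between -0.005 and 0.001.

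**Cross-check of the mechanism.** In one replication the actual SD of the log odds ratio exceeded the average model standard error by 11-14% with equal recruitment, and by 6-7% with skewed sizes or 1036 patients. A Wald test whose standard error is short by a factor r rejects with probability 2·[1 - Φ(1.96/r)]. That is 7.7-8.6% for r = 1.11-1.14 and 6.4-6.7% for r = 1.06-1.07, in line with the simulated levels.

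**The case against.** The strongest objection is that a rule for small centers commonly sits in the statistical analysis plan, which Section 12 promises before the interim analysis and which was not available here. Such a rule would remove the problem. So a reader might infer that the trial as analyzed had an inflated error rate; the protocol does not support that. What stands is narrower: the protocol does not leave the center term open but states an unpooled one, and that model, run as stated, misses its level. A pooling rule elsewhere would depart from Section 12.2.2, so the text needs correcting either way.

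Second, the size depends on recruitment. A reader might take 7.5% as a fixed figure, but it belongs to roughly equal centers. The center count is approximate, and Section 9.5 lets centers be closed for slow recruitment. Uneven or fewer centers, or the 1036-patient maximum, bring the excess down, though it rarely disappears.

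Third, a reader might infer that the odds ratio favors the drug whatever the truth. It does not: with no effect the estimate is centered on 1, and the exaggeration appears only when an effect exists.

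Fourth, one might expect worse for rarer secondary endpoints. No such endpoint was simulated, and the synopsis treats the secondary analyses as descriptive, so no confirmatory claim rests on them.

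Finally, adjusting for center is a reasonable choice after center-stratified randomization. The objection here is to 150 separate intercepts, not to adjustment.

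**Conclusion.** The point holds. With about 5 evaluable patients per center, the primary model as written gives the gatekeeping 5 mg test a type I error of about 6-7.5%, not 5%. Because the 5 mg and placebo arms are of equal size, false rejections are symmetric under the null, so false claims of benefit occur at about 3-3.75% against a nominal 2.5%. When the true odds ratio is 1.86, the model reports about 2.0-2.1.

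These sizes rest on ordinary maximum likelihood with no pooling, and on assumed block size, center sizes and between-center variation. The direction was the same in every setting examined; the amount is not fixed by the protocol. The protocol's sample size and power figures are not in dispute.

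**What to change.** In Section 12.2.2 and the synopsis, and through the cross-reference in Section 12.2.3, replace center by pooled center. Combine centers within country or region by a rule fixed before unblinding, into about 15-25 strata of roughly 30 or more evaluable patients each. The counts fit: 800/25 = 32 and 800/15 = 53 per stratum, while a minimum of 30 allows at most 26 strata (800/30 = 26.7). The choice within that range is the sponsor's.

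In simulation, pooling gave a type I error of 4.6-5.4% with 15 groups and 5.0-5.8% with 25, an odds ratio of about 1.9, and power of about 80-83%, the same as for the model as written. The 15 groups simulated were arbitrary sets of ten centers; pooling by region was not simulated separately.

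A Mantel-Haenszel analysis stratified by center can be kept as a sensitivity analysis. It holds the level but has only about 73-77% power, so it is a poor choice for the primary test.

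The cost is one changed sentence and a pooling rule, with coarser adjustment than the center-level stratification of the randomization. No extra data or patients are needed.

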### **12.2.3 Secondary efficacy variables**

The following secondary efficacy variables will be analyzed for OC and/or LOCF in the FAS:

- Pain-free status at 15 minutes and at 1, 2, 3, 4, and 24 hours post treatment;
- Headache response at 15 minutes and at 1, 2, 3, 4, and 24 hours post treatment;
- Sustained headache response at 2 hours subsequent to a 1-hour headache response;
- Presence of associated symptoms of photophobia, phonophobia, or nausea at 15 minutes and at 1, 2, 3, 4, and 24 hours post treatment;
- Resolution of associated symptoms of photophobia, phonophobia, or nausea at 15 minutes and at 1, 2, 3, 4, and 24 hours post treatment;
- Incidence and time to use of rescue medication up to 24 hours post treatment;
- Ability to perform normal activities at 15 minutes and at 1, 2, 3, 4, and 24 hours post treatment.
- Headache recurrence 2 to 24 hours post treatment;
- Bilateral headache (yes/no) at 15 minutes and at 1, 2, 3, 4, and 24 hours post treatment;
- Intensity increased by movement (yes/no) at 15 minutes and at 1, 2, 3, 4, and 24 hours post treatment.

For the binary secondary efficacy variables, the same logistic regression model as for the analysis of primary efficacy variable will be used. Time to use of rescue medication will be displayed graphically using Kaplan-Meier curves by treatment group. Comparison of treatment doses versus placebo will be based on the Cox proportional hazard model. The secondary endpoints will be analyzed at the 2-sided 5% significance level without any multiplicity correction.

### **12.2.4 Secondary safety variables**

The following secondary safety variables will be analyzed in the safety analysis set:

- Incidence, nature and intensity of AEs;

- Vital signs;
- Laboratory assessments;
- ECG;
- Suicidal risks (C-SSRS).

Change from baseline will be calculated for laboratory, ECG, and vital signs variables. Flags for high/low for laboratory measurements, ECG, and vital signs will also be created based on project reference ranges.

### **12.3 Determination of sample size**

A total of 2400 patients will be enrolled to ensure 1000 randomized patients. This assumes a 56% drop-out rate prior to randomization. Assuming 20% of the randomized patients drop out before treatment of a headache attack, 800 patients (250, 150, 150, and 250 patients in the placebo, zolmitriptan 0.5 mg, zolmitriptan 2.5 mg, and zolmitriptan 5 mg treatment arms, respectively) will be evaluable for the primary analysis. This will give 80% power to detect a treatment difference at the 2-sided significance level of 0.05 if the true difference between a zolmitriptan 5 mg treatment and placebo in terms of difference in pain-free rates is 0.11 for the primary endpoint, 2-hour pain-free status. The power to detect a treatment difference between zolmitriptan 2.5 mg and 0.5 mg versus placebo will be 67% if the true treatment difference is 0.11. A 2-treatment, continuity-corrected, chi-square test of equal proportions is used as an approximation for the intended analysis approach in the power calculations. A difference of 0.11 in response rates is considered a clinically relevant effect. The pain-free rate for the placebo treatment group is assumed to be the same as in a previously conducted study (D1221C00005) on zolmitriptan nasal spray in adolescent patients for both periods combined, 0.18.

Since the assumptions for the sample size calculations are uncertain, an interim analysis is planned for after approximately one third of the planned patients have been treated. The sample size will be re-estimated at the interim analysis using a blinded estimation of the observed total 2-hour pain-free status. The sample size can increase depending on the interim results; the maximum number will be 1036 evaluable patients in total, ie, approximately 1295 patients need to be randomized and 2943 patients need to be enrolled.

The interim analysis will be performed by an independent statistician who is not involved with this trial.

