**Figure 1 Study flow chart**

### 3.2 Rationale for study design, doses and control groups

The study design was selected because it is an easy, simple design of high quality and interpretable results. Adolescents must be aged 12 to 17 years at the time of screening and will not be enrolled if they turn 18 years of age at the time of randomization. This is consistent with the FDA guidelines.

Patients must be able to differentiate between migraine and non-migraine headaches to ensure they are able to participate in the protocol. Patients with a history of a minimum of 2 migraine attacks (moderately or severely disabling) per month are included to maximize the chance of a migraine occurring during the study period.

To address the differences in migraine diagnosis between adolescents and adults, this study will use both the International Headache Society (IHS) and International Headache Society-Revised (IHS-R) (Winner et al 1997) criteria in the inclusion criteria. As patients mature, their migraines become more adult-like, thus the use of both criteria will capture the appropriate population across the age range. IHS-R is the most robust diagnostic tool, incorporating the expanded symptoms complex for pediatric and adolescent migraine. If a patient satisfies the IHS criteria, then by definition he/she will satisfy the IHS-R criteria.

Doses of 0.5, 2.5, and 5 mg of zolmitriptan nasal spray have been selected for this trial. Patients are randomized to the different treatment arms with different probabilities. It is believed that the probability to show a treatment effect is greatest for the zolmitriptan 5 mg treatment arm; hence, this treatment arm is powered with 80% to be able to detect a true difference of 0.11 between placebo and zolmitriptan 5 mg. However, in order to be able to perform the study with a reasonable number of centers, the 2 other zolmitriptan arms are powered at a lower power, ie, 67% power to detect a treatment difference of 0.11 versus placebo. It is anticipated that the true treatment difference with an effective dose might be as large as 0.15 with this study design, including the enriched population obtained by the enrollment period and placebo challenge treatment. With a true difference of 0.15, there will be 90% power to detect a difference for the 2 lower doses compared with placebo and 96% power for zolmitriptan 5 mg versus placebo.

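### The 67% and 90% power stated for 2.5 mg and 0.5 mg are stand-alone pairwise figures; through the planned step-down sequence the power is lower, mainly for 0.5 mg

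*Protocol*

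**What the plan says.** Protocol section 12.3 plans "800 patients (250, 150, 150, and 250 patients in the placebo, zolmitriptan 0.5 mg, zolmitriptan 2.5 mg, and zolmitriptan 5 mg treatment arms, respectively") as evaluable. For 5 mg against placebo it states: "This will give 80% power to detect a treatment difference at the 2-sided significance level of 0.05", given a true difference of 0.11. For the other two doses it states: "The power to detect a treatment difference between zolmitriptan 2.5 mg and 0.5 mg versus placebo will be 67" percent at the same difference. The synopsis repeats these figures. Section 3.2 repeats the 67% and adds a more optimistic case: "With a true difference of 0.15, there will be 90% power to detect a difference for the 2 lower doses compared with placebo", with 96% for 5 mg.

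The synopsis and section 12.3 name the basis of the calculation as a two-treatment, continuity-corrected chi-square test, used as an approximation to the intended analysis.

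The testing rule is in section 12.2.2 and in the synopsis. The order is 5 mg, then 2.5 mg, then 0.5 mg, each at the two-sided 5% level, and testing stops at the first failure: "If the first comparison between zolmitriptan 5 mg and placebo is not significant, then the zolmitriptan 2.5 mg is not to be compared with placebo", and likewise for 0.5 mg after 2.5 mg. The protocol nowhere gives the power through this sequence, and nowhere says that the 67% or 90% leaves the sequence out of account.

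**The concern.** In a fixed sequence, a lower dose can be declared effective only if every earlier comparison is also significant. The relevant probability is a joint one. It cannot exceed the stand-alone power of the dose in question, and it falls with each step. A single figure for both lower doses also hides that they stand at different places in the order.

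The primary objective covers all three doses, and section 1.3 gives as a goal finding the highest and lowest safe and efficacious dose. Section 3.2 accepts reduced power for the two lower doses so that the number of centers stays reasonable, and the figure it accepts is 67%. Anyone weighing that trade-off, or later interpreting a missing result for 0.5 mg, needs the power of the analysis that will actually be run.

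**Working it through.** **Inputs.** Evaluable patients are 250 placebo, 150 for 0.5 mg, 150 for 2.5 mg and 250 for 5 mg (12.3). The placebo pain-free rate is taken from the earlier study "on zolmitriptan nasal spray in adolescent patients for both periods combined, 0.18" (12.3). Base case: "A difference of 0.11 in response rates is considered a clinically relevant effect" (12.3), so the active rate is 0.18 + 0.11 = 0.29. Optimistic case: "It is anticipated that the true treatment difference with an effective dose might be as large as 0.15" (3.2), so the active rate is 0.18 + 0.15 = 0.33. Two-sided alpha is 0.05.

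**Step 1: reproduce the stated figures.** With n0 and p0 for placebo, n1 and p1 for the dose, and p the pooled rate:

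power = Φ{ [ (p1 − p0) − c − 1.96·s0 ] / s1 }

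where c = ½(1/n0 + 1/n1), s0 = √[p(1 − p)(1/n0 + 1/n1)] and s1 = √[p0(1 − p0)/n0 + p1(1 − p1)/n1].

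- 5 mg at 0.11: c = 0.0040, p = 0.235, s0 = 0.03792, s1 = 0.03760. Then (0.1100 − 0.0040 − 0.0743)/0.03760 = 0.842, giving 80.0%.
- Lower dose at 0.11: c = 0.0053, p = 0.22125, s0 = 0.04287, s1 = 0.04431. Then (0.1100 − 0.0053 − 0.0840)/0.04431 = 0.466, giving 67.9%.
- The same formula at 0.15 gives 96.5% for 5 mg and 90.2% for a lower dose.

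The stated values are 80%, 67%, 96% and 90%, so all four agree within about one point. Without the continuity correction they would be 82.9%, 72.1%, 97.2% and 92.1%, so the protocol used the correction. This confirms that the 67% and 90% are stand-alone pairwise powers.

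**Step 2: power through the sequence.**

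- Power for 2.5 mg = P(5 mg significant and 2.5 mg significant).
- Power for 0.5 mg = P(all three significant).

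The comparisons share the placebo arm and are positively correlated, so multiplying the stand-alone powers would overstate the loss. The joint probabilities were therefore simulated: 1,000,000 trials, one shared placebo arm, binomial counts, the same continuity-corrected test, and benefit required. The simulated stand-alone powers were 80.4% and 68.2% at 0.11, and 96.6% and 90.4% at 0.15, in line with step 1.

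| True difference (5 / 2.5 / 0.5 mg) | 2.5 mg, stated | 2.5 mg, through sequence | 0.5 mg, stated | 0.5 mg, through sequence |
|---|---|---|---|---|
| 0.11 / 0.11 / 0.11 | 67% | 59.5% | 67% | 46.9% |
| 0.13 / 0.11 / 0.11 | 67% | 64.8% | 67% | 50.0% |
| 0.15 / 0.11 / 0.11 | 67% | 67.2% | 67% | 51.2% |
| 0.15 / 0.15 / 0.15 | 90% | 88.2% | 90% | 81.6% |

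For comparison, simple multiplication in the first row would give 0.804 × 0.683 = 54.9% for 2.5 mg, which is too low.

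**Step 3: checks.** A multivariate normal calculation that starts from the protocol's own 80% and 67%, with the shared-placebo correlation, gives 57.5% and 43.7% at 0.11. From 96% and 90% it gives 87.1% and 79.9% at 0.15. Simulation without the continuity correction gives 64.0% and 51.8% at a common 0.11, and 90.4% and 84.8% at a common 0.15. The corresponding uncorrected stand-alone powers are about 72% and 92%.

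**Step 4: could 67% be meant as conditional power?** Once the earlier steps have succeeded, the power at a common 0.11 is 59.5/80.4 = 74% for 2.5 mg and 46.9/59.5 = 79% for 0.5 mg. The 67% is therefore neither the power through the sequence nor the power once a dose is reached.

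**The case against.** The strongest reply is that nothing has been miscalculated. The protocol names a two-treatment test as the basis of its power figures, section 12.2.1 says that pairwise comparisons are the primary analysis, and the figures reproduce. That stands: a reader might infer an arithmetic error, and there is none. What remains is that the figures are presented as the power to detect an effect, beside a testing rule that can prevent the test, without a label that connects the two.

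Second, 60% and 47% assume that all three doses have the same effect. The protocol's power statements do use one common difference, but section 3.2 also expects 5 mg to be the dose most likely to show an effect. With 5 mg at 0.15 and the lower doses at 0.11, 2.5 mg keeps its 67%. This stands too, and the result must be given as a range. It does not rescue the 0.5 mg figure, which reaches only 51%.

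Third, the lower power was a deliberate and disclosed choice, and the sample size and its re-estimation are driven by 5 mg against placebo. That limits the consequence to wording. It does not make 67% the right description of the power accepted.

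**Conclusion.** The stated 67% (synopsis, 3.2, 12.3) and 90% (3.2 only) overstate the chance that the planned analysis declares a lower dose effective. With the lower doses at 0.11, the power through the sequence is about 60 to 67% for 2.5 mg and 47 to 51% for 0.5 mg, depending on whether 5 mg has 0.11 or up to 0.15. For 0.5 mg the shortfall is 16 to 20 points against the stated 67%. At a common 0.15 it is about 8 points against the stated 90%.

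Three stronger readings are not supported:

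- That 0.5 mg is more likely to fail than to succeed at an effect of 0.11. The figure is 46.9% with the continuity correction and 51.8% without it. The planned analysis is a logistic regression, for which the corrected test is only a planning approximation. Roughly an even chance is as much as can be said.
- That the 90% for 2.5 mg is materially wrong. It becomes 88.2%, or 90.4% without the correction.
- That the type I error control or the arm sizes are faulty. Nothing here bears on either.

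The figures rest on a placebo rate of 0.18 and 800 evaluable patients, before any increase from the blinded re-estimation. They do not model the center term of the logistic regression.

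**What to change.** In the synopsis, 3.2 and 12.3, label 67% as the unconditional pairwise power for each lower dose. Add the power through the sequence at 0.11: about 80% / 60% / 47% for 5 / 2.5 / 0.5 mg if all doses have the same effect, and about 65 to 67% and 50 to 51% for 2.5 mg and 0.5 mg if 5 mg has 0.13 to 0.15. State the equal-effect assumption and the test used.

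In 3.2 only, label the 90% in the same way and add about 96% / 88% / 82% at a common 0.15.

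No change to sample size, test, testing order or alpha is needed. The only cost is that the stated figures become less favorable.
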